3 INVESTIGATIONAL PLAN

3.1 General Schema of Study Design

This is a three arm, randomized control trial study to assess the marginal effects of different strategies of financial incentives for ICS use targeting a cohort of children with high risk asthma.

3.1.1 Screening Phase

Potential subjects will be screened through the daily census listings for the inpatient units on the Epic medical record at CHOP using the protocol inclusion and exclusion criteria. Epic alerts and patient lists identifying high risk children with asthma will assist research staff in screening potential subjects.

Eligible children and their caregivers will be recruited during an asthma hospital admission, whenever possible, or in the month following hospital discharge, if the study team is unable to reach the family during the hospitalization. In the latter circumstance or if the child is eligible through asthma related outpatient visits, the study team will contact eligible participants by phone and if the caregiver expresses interest, the study team will approach the caregiver and child for informed consent/assent at a follow-up visit or via phone, if in-person recruitment is not feasible.

Parental/guardian permission (informed consent) and, if applicable, child assent, will be written on a physical copy of the consent form, when consent/enrollment takes place in person, prior to any study related procedures being performed. In the circumstance of telephonic enrollment, electronic consent via the REDCap platform will be obtained prior to any study related procedures.

If subjects consent to enrollment, the Study Run-in Phase will begin on the day of enrollment.

3.1.2 Run-in Phase (Month 0)

The study will be broken down into three discrete phases: (1) *Run-in* (2) *Experiment*, and (3) *Observation* (Figure 2). During the *Run-in* phase, every caregiver-child dyad will have access to the inhaler sensor app and will receive electronic ICS use monitoring. ICS use will be monitored using an electronic sensor that affixes to their ICS inhaler and will remain through the study *Observation* phase. Participants will be sent 4 text messages, each designed to elicit a response from the caregiver about the study technology or the study itself. (See Appendix 1 for content of the Run-in text messages) Participants for whom any inhaler use data is transmitted to the study platform within the first 2 weeks of the Run-in Phase AND reply to one or more of the 4 text messages sent from the study platform (“Responders”) will be randomized into one of three arms at the end of the Run-in phase. (see section 4.10 for details on procedures for “Non-responders”) The second two weeks of the Run-in Phase is designed to provide baseline adherence data.

[figure not shown]

Figure 2: Study schema for proposed RCT

3.1.3 Experiment Phase (Months 1-3) and Observation Phase (Months 4-6)

The three experimental conditions will be: financial incentives, adherence reminders, and feedback (Arm 1); adherence reminders and feedback without incentives (Arm 2); or electronic monitoring alone (Arm 3). The financial incentives in Arm 1 will consist of 3 months of fixed-ratio incentives for each ICS actuation (i.e. 25 cents per puff for children on 4 daily ICS doses and 50 cents per puff for children on 2 daily doses), with a maximum of \$1 per day. With regard to the reminders and feedback in Arms 1 and 2, study participants will receive automated daily text message or push notification reminders and automated weekly feedback summarizing their adherence performance through Way to Health, a mobile health, electronic monitoring platform (described below in section 4.1). At the end of the first month of the experiment phase, families will be contacted by study staff to complete a follow-up survey that will reassess disease control, medication supply, and intentions and behaviors with

regard to ICS use (study visit 2). After the experiment interval, families will be contacted again by study staff to complete a follow-up survey and a semi-structured interview (study visit 3). At this point, all reminders, feedback, and incentives will cease, but daily ICS use monitoring will continue with the electronic sensors for all study arms (*Observation* phase) to assess for enduring effects. There will be a fourth study visit in the 7th study month, when study surveys will be completed, and a fifth and final study visit at one year assessing asthma control and health care utilization outside of the CHOP system.

For participants receiving adherence incentives in the experiment phase, accrued incentive value will be summed at the end of each 30-day interval (maximum \$30) and added to a debit card that will be provided to the child upon enrollment. In the experiment phase, children randomized to Arms 2 and 3 who have any actuations recorded in the experiment phase will receive a \$10 disbursement at the end of each month of the Experiment phase. Children in all 3 study arms will receive a \$10 disbursement for each month during the Observation phase for which any adherence data (for the prior month) is transmitted to the platform. This compensation will not be contingent upon the participant's ICS adherence. Separate study visit compensation (\$20) will be provided to the caregiver after enrollment and the 4th study visit, as well as after follow-up visits/calls at two, four, and 12-months.

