4.9 Visit 5 (clinic or telephone) – month 12-13

- Study visit 5 survey question blocks (see section 4.11.2)

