4.15 Secondary Endpoints

Secondary endpoints will include the following:

- Adherence to ICS regimen in *Observation* interval (months 4-6)
- Adherence trajectory, as determined by group-based modeling of adherence patterns.
- Change in cACT score from first study visit to the second, third, fourth, and fifth study visits.
- Number of asthma-related emergency room visits, hospitalizations, and oral steroid courses between study conditions.
- Healthcare costs associated with emergency room visits, hospitalizations, and oral steroid courses between study conditions.
- Continued use of sensors in 7-13 month follow-up period (feasibility outcome)

Health system use outcomes will be assessed primarily using CHOP electronic health record data and, secondarily, via caregiver report to account for utilization that may have occurred outside of CHOP. ED visits, hospitalizations, and oral steroids courses will be characterized as asthma-specific using existing, validated asthma registry definitions that include asthma visit diagnoses, medication orders, and asthma pathway order set activation. Costs will be estimated using average insurance payments for asthma ED visits, hospitalizations, and oral steroid courses in addition to the costs of the intervention components (i.e. sensors, incentive value, and research staff support).

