4.18 Additional analyses

Hypothesis 1.2 Longer time intervals to next asthma-related ED or inpatient visit, and reduced healthcare use and costs, will be observed in Arm 1 compared to Arms 2 and 3 (and in Arm 2 compared to Arm 3).

Time to next asthma-related ED or inpatient visit from enrollment will be first modeled using the Kaplan-Meier plots. Study arms will be compared using log-rank tests and unadjusted Cox proportion hazards models. Adjusted hazard models will include the additional covariates described above and the Anderson-Gill method will be used to account for recurrent events. Total medical costs will be estimated for the 12 months following study enrollment, accounting for each asthma-related ED visit and hospitalization, as well as the expenses incurred with study participant incentives, sensors, and use of the WTH automated platform. We predict that intervention will reduce medical costs, thereby contributing to a *cost offset*. We will estimate potential savings in medical costs by calculating the difference in average total medical costs minus study-related expenses between study arms.

Aim 2. Assess proposed mechanisms by which intervention strategy influenced adherence trajectory.

Aim overview: The broad goal of this aim is to assess which participant and study characteristics are associated with different longitudinal adherence trajectories.

Characteristics to be examined include baseline factors (demographic, clinical, and prior health utilization factors), intervention strategy (study arm), and potentially modifiable behavioral characteristics. Of specific interest is how intervention strategy in the Experiment phase (study arm) influences child asthma self-efficacy, shared medication responsibility, and medication habit over time and how these characteristics vary with longitudinal ICS adherence trajectories. [Figure 4]

Hypothesis 2: Increases in (1) participant self-efficacy, (2) shared medication responsibility, and (3) habit score will partially mediate the relationship between study arm and sustained adherence trajectory.

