Protocol deviations will be identified by PI and research project manager and reported to the CHOP IRB through the electronic IRB reporting system in accordance with CHOP IRB policy. These events will be presented to the DSMB and reported to the research team at regularly scheduled study meetings.

Safety Monitoring:

An adverse event (AE) includes any event meeting the following definition:

Any untoward or unfavorable medical occurrence in a human subject, including any abnormal sign (for example, abnormal physical exam or laboratory finding), symptom, or disease, temporally associated with the subject's participation in the research, whether or not considered related to the subject's participation in the research (modified from the definition of adverse events in the 1996 International Conference on Harmonization E-6 Guidelines for Good Clinical Practice).

A Serious Adverse Event (SAE) is defined as any untoward medical occurrence that:

- Results in death
- Is life-threatening
- Results in a persistent or significant disability/incapacity
- Results in in-patient hospitalization or prolongation of existing hospitalization
- Results in a congenital anomaly/birth defect.
- Important medical events that may not result in death, be life threatening, or require hospitalization may be considered a SAE when, based upon medical judgment, they may jeopardize the patient or participant and may require medical or surgical intervention to prevent one of the outcomes listed in this definition.

[figure not shown]
Safety data collection:

Information regarding unanticipated problems and adverse events (AE) and serious adverse events (SAE) will be collected at each study visit through follow-up questionnaires. Once the adverse event has been identified, determined to be unexpected, and at least potentially related to the research study, appropriate CHOP IRB electronic forms will be completed and submitted to the IRB.

Safety data reporting:

Events identified will be recorded and reported to the CHOP IRB. These events will be presented to the DSMB and reported to the research team at regularly scheduled study meetings. Led by the PI, the research team will review each event and make appropriate safety decisions.

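### Care outside CHOP is named as a question only at the one-year visit, so the supplement to the utilization endpoints rests on about a year of recall and is not scheduled for families lost earlier

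*Combined protocol and SAP*

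**What the plan says.** Section 4.15 sets two sources for utilization. "Health system use outcomes will be assessed primarily using CHOP electronic health record data", and then, "secondarily, via caregiver report to account for utilization that may have occurred outside of CHOP". It gives no collection times, recall window or rule for combining the sources.

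Section 3.1.3 gives the visit content. Visit 2 covers disease control, medication supply and ICS intentions and behaviors. Visit 3 is a survey plus an interview. For Visit 4 it says only: "There will be a fourth study visit in the 7th study month, when study surveys will be completed". Outside-CHOP use appears for the first and only time at Visit 5: "a fifth and final study visit at one year assessing asthma control and health care utilization outside of the CHOP system". Table 1 puts Visits 2 to 5 at months 2, 4, 7 and 12-13.

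Sections 4.2 to 4.9 refer every visit's survey to Section 4.11.2, which lists self-efficacy, responsibility and habit, with no utilization item for any visit. Section 4.10.1 gives withdrawing families the procedures of Visit 1, 2, 3 or 4.

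Section 4.11.1 abstracts the number and dates of asthma ED visits, hospitalizations and steroid courses from the chart over the 13-month study. Appendix 2 says that adverse events and serious adverse events "will be collected at each study visit through follow-up questionnaires", and it counts any inpatient hospitalization as serious.

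Section 4.18 uses the events: "Time to next asthma-related ED or inpatient visit from enrollment will be first modeled using the Kaplan-Meier plots". Log-rank, Cox and recurrent-event models and 12-month costs follow.

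**The concern.** The caregiver report is there to fill a known gap in a single-hospital record. If it is taken once, at the end, two things follow.

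First, the caregiver must recall about a year of events. Those in the Experiment phase, when the intervention is running, lie furthest back. If such events enter the Section 4.18 models, they need dates, and one year-long recall supplies dates poorly.

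Second, completeness depends on retention. A child who reaches Visit 5 can contribute CHOP and outside events, while a child lost earlier contributes CHOP events and no scheduled utilization report. The plan does not say when outside-CHOP follow-up ends for that child, so unobserved time could be read as time without events.

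These endpoints are secondary and the trial is not powered for them. But Section 4.17 says that the trial is to give preliminary effect sizes on utilization for a future multicenter study, so an incomplete count would carry forward into that design.

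**Working it through.** **1. The plan's own figure.** Section 4.17 gives 65% against 35%, 80% power, alpha 0.05 and about 20% loss; Section 4.16.2 makes tests two-sided. With unpooled variance:

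(1.960 + 0.842)² × (0.65 × 0.35 + 0.35 × 0.65) / 0.30² = 39.7, so 40 per arm.

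40 / (1 − 0.20) = 50, and 50 + 25 + 50 = 125.

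The figure reproduces and is not in dispute. It matters here only as the source of the 20%, which was set for the Arm 1 against Arm 3 adherence comparison in months 1-3, not for attendance at months 12-13.

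**2. Where the question is named.**

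| Contact | Month | Outside-CHOP use named? |
|---|---|---|
| Visit 2 | 2 | No |
| Visit 3 | 4 | No; survey not itemized |
| Visit 4 | 7 | No; survey not itemized |
| Visit 5 | 12-13 | Yes (Section 3.1.3) |
| Early termination | any | No; Visits 1-4 procedures |

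**3. Recall length.** With one question at Visit 5, recall from enrollment is 12-13 months, or about 11-12 from randomization after the one-month run-in. With a question at each visit, the gaps are 2 − 0 = 2, 4 − 2 = 2, 7 − 4 = 3, and 12 − 7 = 5 to 13 − 7 = 6 months. The longest falls to 5-6 months.

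**4. Children without the Visit 5 report (assumption: the 20% applies to Visit 5).** 0.20 × 125 = 25, or 10, 5 and 10 in Arms 1, 2 and 3.

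**5. Follow-up time covered by a caregiver utilization report.** Let a proportion d be lost before Visit 5.

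- Question at Visit 5 only: covered share = 1 − d.
- Question at every visit, loss spread evenly from month 0 to month T: covered share = Σ (gap length) × (1 − d × visit month / T) / T.

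For d = 0.20 and T = 12: (2 × 0.967 + 2 × 0.933 + 3 × 0.883 + 5 × 0.80) / 12 = 10.45 / 12 = 87%. T = 13 also gives 87%.

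If all losses come before Visit 2, the share stays at 80%. If all come after Visit 4, it is (7 + 5 × 0.80) / 12 = 92%, or (7 + 6 × 0.80) / 13 = 91%.

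| Assumed loss | Visit 5 only | Every visit, even loss |
|---|---|---|
| 10% | 90% | 93-94% |
| 20% | 80% | 87% |
| 30% | 70% | 80-81% |

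These are shares of time asked about, not of events missed. The documents do not give the share of asthma care outside CHOP, so no undercount follows from them.

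**The case against.** The strongest reply is that silence is not absence. Section 4.11.2 is plainly incomplete: it omits the utilization item even for Visit 5, and it omits the asthma control test that Table 1 schedules at every survey visit. The surveys at Visits 3 and 4 are not itemized. A reader might infer that caregivers are definitely not asked before Visit 5. The documents support only that no earlier question is named.

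A reader might also infer that children lost early have no outside-CHOP data at all. That goes too far. The safety questionnaires at each visit should bring out some outside hospitalizations up to the last visit attended. They do not clearly cover outside steroid courses or treat-and-release ED visits, and nothing links them to Sections 4.15 or 4.18.

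CHOP events, with dates, are the primary source and need no visit attendance. Section 4.18 does not say that caregiver-reported events enter the survival models. The weakness therefore touches the supplement, not the core of the endpoint.

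A third inference is that retention will differ by arm and create a false difference in utilization. Families are unblinded, and child payments differ in the Experiment phase (up to $30 a month in Arm 1, $10 in Arms 2 and 3). But caregivers in all arms receive the same $20 per visit, and performance pay ends after month 3. Differential retention is possible, but no document figure shows it.

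What stands after all this is the schedule as written: one named question, a year late, omitted at early termination.

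**Conclusion.** The point holds as a cheap improvement to secondary endpoints, not as a demonstrated bias. As written, the outside-CHOP supplement depends on 12-13 months of recall and is not scheduled for families who leave before Visit 5. This assumes that no unlisted survey item asks earlier; if one does, the protocol should say so.

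The figure of up to 25 of 125 is an illustration that moves the roughly 20% loss from the adherence comparison to Visit 5. It is not the protocol's forecast of Visit 5 non-completion. Under that assumption and even loss over time, asking at every visit raises the follow-up time covered by caregiver report from 80% to about 87% (80% to 92% depending on when losses occur). The shorter recall does not depend on any loss assumption.

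**What to change.** - **Collection.** At Visits 2, 3 and 4 and at early termination, as well as at Visit 5, ask about asthma ED visits, hospitalizations and oral steroid courses outside CHOP since the last contact, with approximate dates. List the item in Section 4.11.2 and add it to Section 4.10.1.
- **Primary ascertainment.** Keep the EHR-only analysis for all randomized children.
- **Combined analysis.** Report EHR plus caregiver events alongside it. End each child's follow-up in that analysis, for both sources, at the last completed survey, so that each child has one follow-up clock.
- **Linkage.** State in Section 4.15 how EHR, caregiver and safety-questionnaire events are matched by date and duplicates removed.

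The cost is a few more minutes on surveys already scheduled and paid for, and one additional analysis. Two limits remain. The combined analysis discards EHR time after the last survey, which is why it should not replace the EHR-only result. Families who withdraw may also have earlier responses removed (Section 4.10.1), so the gain is mainly for those who lose contact or withdraw without asking for removal.

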3.1.4 Follow-up Phase

After completion of the *Observation* interval, participants will enter into a follow-up phase. Participants will complete a brief final study survey at during months 12-13 with study staff. The study team will also assess the number of ED visits, hospitalizations, and oral steroid courses for asthma at CHOP over this time period within the CHOP EMR. Electronic monitoring of daily ICS medications will continue during the follow-up phase to assess for ongoing feasibility and acceptability of electronic monitoring, if the data is available.

3.2 Allocation to Treatment Groups and Blinding

Following consent, confirmation of eligibility, and the study Run-in phase (2-weeks to confirm that the participants' technology is functioning appropriately and 2-weeks to collect baseline data on the participants' adherence), patients will be assigned to one of three arms for the *Experiment* phase of the study using a 2:1:2 randomization scheme.

3.3 Study Duration, Enrollment and Number of Sites

3.3.1 Duration of Study Participation

The study duration will be up to 13 months, beginning with screening and enrollment on day 1 and continuing through the study completion visit at the end of the follow-up period at 12-13 months.

3.3.2 Total Number of Study Sites/Total Number of Subjects Projected

The study will be conducted at CHOP alone.

We plan to enroll approximately 125 child-parent dyads. For our funder, enrollment will be reported as randomization into experiment phase.

3.4 Study Population

3.4.1 Inclusion Criteria

- 1) Males or females age 5 to 12 years and their parent or legal guardian.
- 2) Caregiver has an app enabled cellular phone (i.e., smartphone)
- 3) Prescribed inhaled corticosteroid or corticosteroid/long acting beta agonist combination for daily use
- 4) At least 2 asthma exacerbations in the preceding year (Any combination of hospitalizations, ED visits, or outpatient visits where oral steroid courses were administered for asthma)
- 5) Parental/guardian permission (informed consent) and if appropriate, child assent.

